**Outcomes of Epidural versus Combined Spinal and Epidural (CSE) Anesthetic
Technique on the Success of Trial of Labor after Cesarean (TOLAC): A pilot study**

NCT02105558

Version Date: 03/24/2014

Department of Anesthesiology

Scholarly Research Project Submission Form

Name(s): [name] (PI), [name], FRCA (co PI)

Faculty Mentor: [name], FRCA

Category of Research: Prospective randomized clinical pilot study

Expected length of time for Project: One year or until 60 patients have been enrolled

Title of Research Project: Outcomes of Epidural versus Combined Spinal and Epidural (CSE) Anesthetic Technique on the Success of Trial of Labor after Cesarean (TOLAC): A pilot study

Summary of Project: To compare the effects of epidural versus CSE anesthesia on the success of TOLAC. This will be a prospective clinical study randomizing 60 eligible women into either an epidural group or CSE group. The effects of the specific regional anesthetic on patient's individual labor efforts will then be closely monitored. Written informed consent shall be obtained to enroll the patients in either group. Pain scores and electronic medical record information will be used with non-identifiable coding to determine the resulting outcomes.

Background:

Though it has been said, "once a cesarean, always a cesarean," the current medical stance has changed and now encourages VBAC in a select population of patients. VBAC has several advantages over a repeat cesarean including decreased recovery period, decreased risk of infection, avoidance of major abdominal surgery, and lessened blood loss (1). Predictors for success of VBAC include previous spontaneous vaginal birth, singleton pregnancy, and previous low transverse scar for C-section delivery (1). TOLAC is a reasonable option for select pregnant women and is associated with a 74% likelihood of VBAC (3). Risk factors for failure of VBAC include labor dystocia, advanced maternal age, maternal obesity, fetal macrosomia, GA>40 weeks, short inter pregnancy interval, and preeclampsia (1).

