When the patient on the obstetric service requests an epidural for labor analgesia, a consult is immediately placed to the Anesthesia service. Patients who request neuraxial anesthesia for labor analgesia will then be screened for the study. Written informed consent shall be obtained from the patient prior to enrollment in this prospective randomized clinical study. The regional anesthetics will be placed by the obstetrical anesthesia team at Lyndon B. Johnson Hospital, a well-established partner of the University of Texas Medical School at Houston and a facility capable of performing an emergent C-section if necessary. Patients shall be randomized via computer generated randomization sequence and assigned a separate study number different from their medical record number. The study code and MRN will be saved on a linking log on a password protected drive. Standard ASA monitors will be applied to all patients including NIBP, pulse oximetry and fetal heart monitors. Patients will be bolused with 1 liter of LR prior to the procedure via intravenous catheters. In the epidural group, epidurals will be placed in a sterile fashion using a 17g Tuohy needle to locate the epidural space via loss-of-resistance to saline at the lumbar vertebral level. 3 ml of 1.5% lidocaine with 5ug/ml of epinephrine will then be used for test dose to exclude intrathecal or intravenous placement of the catheter. Epidural solution composed of 5ml of 0.2% ropivacaine and another 5 ml of 0.2% ropivacaine will then be administered. In the CSE arm, the epidural space will again be located with a 17g Tuohy needle and dural puncture performed with 25g Pencan needle via needle-through-needle technique. Spinal injection of 2ml 0.2% ropivacaine will then be performed and spinal needle removed. An epidural catheter will then be placed and test dose performed with 3 ml of 1.5% lidocaine with 5ug/ml of epinephrine. Maintenance dose will be via an epidural pump using 0.2% ropivacaine at a rate of 12 ml/hr. Self-determined numeric pain scores will be obtained prior to and after placement of the regional anesthetic and after delivery by nursing staff. Analgesia will be considered successful if the numerical pain score value is 3 or less.

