Data collection will be performed via pain scores obtained prior to and following placement of the regional anesthetic and establishment of analgesia, along with data on maternal satisfaction. Electronic medical records will also be used to gather the resulting outcomes.

Data to be collected:

Demographics:

- age
- weight
- height
- ethnicity
- gestational age
- reason for previous cesarean/incision type if known
- previous SVD
- pregnancy number
- cervical dilation at/near time of block (performed by obstetrician)
- estimated fetal weight

Pain scores:

- before RA
- 15 minutes, 30 minutes, and 60 minutes after RA
- 24 hours after delivery

Supplementation of catheter boluses for pain relief and total doses given

Side effects of RA:

- pruritus
- nausea
- vomiting
- hypotension
- post dural puncture headache

Neonatal outcome:

- fetal heart rate immediate post regional
- APGARs at 1 min and 5 min

- birth weight

Delivery:

- date and time at which cervix becomes fully dilated (performed by obstetrician)
- date and time at which the following occur:
 - SVD
 - c-section
 - instrumentation

Maternal Satisfaction

- pain relief
- childbirth experience

Data Analysis Plan:

Power Analysis

Our null hypothesis is that there is no difference in success of VBAC between epidurals and CSEs for women undergoing TOLAC. Our alternative hypothesis is that CSE will result in more successful VBAC than will epidurals. The success rate of VBAC is around 74%. Based on the literature, we expect the success rate with CSE to increase by 20-25%; therefore, given our sample size of 60, we will have 80% power to detect a difference between the two groups.

Primary Outcome

The primary outcome, success for VBAC, will be assessed using χ^2 or the Fisher Exact test, in case of cell sizes <5, to determine if the difference in success rates between the two analgesia groups, CSE and epidural, is statistically significant. Logistic regression analysis will be used to adjust for potential confounders and other factors associated with success or failure of VBAC.

Secondary Outcomes

The secondary outcome, success of analgesia, as measured by pain score on a scale of 1 to 10, will be assessed using ANOVA. Difference in mean pain score between the two groups will be determined in a model with the continuous/count variable pain score as the dependent variable and analgesia group as the independent variable.

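### The stated 80% power is not what the planned chi-square-or-Fisher rule delivers across the assumed 20-25 point benefit; it is met at best near the top of that range

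*Combined protocol and SAP*

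**What the plan says.** All statements are in the combined protocol and SAP.

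- **Data Analysis Plan, Power Analysis.** The control rate: "The success rate of VBAC is around 74" per cent. The effect: "we expect the success rate with CSE to increase by 20-25" per cent. The claim: "given our sample size of 60, we will have 80% power to detect a difference between the two groups". The hypothesis is directional: "Our alternative hypothesis is that CSE will result in more successful VBAC than will epidurals". The section gives no alpha, sidedness, allocation ratio or power formula, and does not say whether the increase is absolute or relative.
- **Data Analysis Plan, Primary Outcome.** VBAC success "will be assessed using χ^2 or the Fisher Exact test, in case of cell sizes <5". It does not say whether observed or expected counts are meant, or whether chi-square carries a continuity correction. Logistic regression is added for adjustment, which does not settle the primary test.
- **Methods.** "Patients shall be randomized via computer generated randomization sequence", with no ratio or blocking.
- **Expected length of time for Project.** "One year or until 60 patients have been enrolled", so 60 is not guaranteed.

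**The concern.** A power figure should describe the test that will be run. Here the test depends on the final table, and the plan's own assumptions make failures so rare in the CSE arm that the small-cell branch is almost always taken. Fisher's test is conservative at these sizes, so an 80% figure that suits an uncorrected chi-square need not suit the rule. The claim is also attached to a range of effects without saying where in the range it applies. What is at stake is how a non-significant result would be read: someone trusting 80% would take it as fair evidence against a 20-point benefit, when the trial had roughly an even chance of detecting one.

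**Working it through.** **Inputs.** From the plan: control rate 0.74, increase 20-25, N = 60, chi-square or Fisher. Assumed because the plan is silent: 5% level, two-sided (one-sided also shown), chi-square uncorrected, increase in percentage points (CSE 0.94, 0.965, 0.99), no dropout, and 30 per arm unless another split is given. Splits are epidural/CSE.

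**1. Reproducing the 80%.** Pooled normal approximation, n per arm:

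power = Φ{[Δ√n − 1.960·√(2p̄(1−p̄))] / √(p₁(1−p₁) + p₂(1−p₂))}

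- +25: (0.25 × 5.477 − 1.960 × 0.4833) / 0.4498 = 0.938, power 82.6%. Solving for n at 80% gives 29 per arm, 58 in all.
- +22.5: power 70.0%.
- +20: (0.20 × 5.477 − 1.960 × 0.5185) / 0.4988 = 0.159, power 56.3%. For 80%, n = [(1.960 × 0.5185 + 0.842 × 0.4988) / 0.20]² = 51.6, so 52 per arm.

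One-sided at 5% the formula gives 68.7%, 80.4% and 89.9%. The stated 80% is therefore reproducible near +25 two-sided, or near +22.5 one-sided, but not at +20.

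**2. Which branch the rule takes.** At 30:30 the mean number of failures is 30 × 0.26 = 7.8 with epidural and 30 × 0.06 = 1.8 (at +20) or 30 × 0.01 = 0.3 (at +25) with CSE. The probability of an observed cell below 5 is 97.1%, 99.7% and 100.0% at the three effects. If expected counts are meant, the mean expected failure count per arm is (7.8 + 1.8)/2 = 4.8 at +20 and (7.8 + 0.3)/2 = 4.05 at +25, and Fisher is used in 50% and 72% of trials.

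**3. Exact power of the rule.** For each split, enumerate every table (a successes of n₁, b of n₂), apply the rule, and sum Bin(a; n₁, 0.74) × Bin(b; n₂, p₂) over the rejecting tables.

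| Test and split | +20 | +22.5 | +25 |
|---|---|---|---|
| Rule, observed counts, 30/30 | 42.2% | 56.9% | 74.7% |
| Rule, expected counts, 30/30 | 48.8% | 60.9% | 75.3% |
| Rule, observed, 29/31 | 55.7% | 73.5% | 90.8% |
| Rule, observed, 31/29 | 46.6% | 61.0% | 77.8% |
| Rule, observed, average over simple randomisation of 60 | 49.3% | 65.3% | 83.1% |
| Rule, expected, same average | 51.6% | 66.5% | 83.3% |
| Rule, observed, one-sided 5%, 30/30 | 55.3% | 70.0% | 85.6% |
| Uncorrected chi-square for every table, 30/30 | 59.8% | 76.7% | 92.3% |
| Barnard, two-sided, pooled score, 30/30 | 55.8% | 71.7% | 89.3% |
| Barnard, 29/31 | 57.9% | 74.5% | 90.9% |
| Barnard, average over simple randomisation | 56.4% | 72.7% | 89.3% |

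The CSE rate at which the two-sided observed-count rule reaches 80% is 99.65% at 30/30, 97.4% at 29/31 and 98.6% on average. At +20 points the highest figure for the rule, under either trigger and either sidedness, is about 63%.

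**4. Where the shortfall comes from.** At +20 and 30/30, chi-square for every table would give 60%. So 80 − 60 = 20 points are due to sample size and effect, and 60 − 42 = 18 to the switch to Fisher. At +25, chi-square would give 92% against 75% for the rule, so there the switch alone takes power below 80%.

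**5. Error rate.** The maximum two-sided size at 30/30 is 5.2% for the rule and 4.7% for Barnard. At 28/32 it is about 5.6% and 4.96%.

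**6. Other readings.** If the increase is relative, CSE is 0.74 × 1.20 = 88.8% to 0.74 × 1.25 = 92.5%. At 30/30 the observed-count rule then has 21-35% power and Barnard 29-47%. If enrolment stopped at 50, the rule's average would be 40/54/71% (absolute reading).

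**The case against.** - **The 80% is not an arithmetic error.** This stands. A standard approximation gives 82.6% at +25 with 58 women needed, and the plan does not say that 80% holds at every point of its range. What it omits is where in the range the figure applies and that it suits a test the rule will rarely select.
- **30/30 is an unfavourable split that the plan never states, and the hypothesis is directional.** Both stand. A reader might infer from the 42-75% at 30/30 that 80% is out of reach anywhere in the range. The documents do not support that: the same rule gives 91% at 29/31, 83% on average and 86% one-sided at 30/30, all at +25.
- **Chi-square with a Fisher fallback is conventional and pre-specified.** It is, and a maximum size of 5.2% at 30/30 is little loss of control. The case here is about power and clarity, not a seriously inflated error rate.
- **The two readings of the trigger might be thought to give opposite verdicts often.** The natural example, 22/30 against 28/30 (Fisher p = 0.080, chi-square p = 0.038), has (8 + 2)/2 = 5 expected failures per arm, exactly on the boundary, and averaged over splits the readings disagree in only 2.3% of trials or fewer. It should carry no weight.
- **Barnard is a preference and does not cure the power gap.** Largely right; it is offered below as optional.

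**Conclusion.** The concern holds in a limited form. The rule named for the primary outcome does not have 80% power across a 20-25 point benefit. Two-sided at 5%, its power runs from 42% to 75% at 30:30 and from 49% to 83% on average under simple randomisation. It reaches 80% at best near +25 points (one-sided testing and some splits help) and in no case examined at +20. The result rests on the absolute reading of the increase, a 5% level, uncorrected chi-square and full enrolment of 60; the relative reading or a smaller N makes it worse. A reader might also infer that a better test would rescue the claim. It would not: even Barnard's test has 56% power at +20, because 60 women are too few for that effect. As the study is a pilot, the correction is inexpensive and optional.

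**What to change.** Before outcomes are seen:

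1. **Restate the power.** Replace the flat 80% with the power of the test that will be run at both ends and the middle of the range, stating alpha, sidedness, the allocation assumed, and that the increase is in percentage points (if so).
2. **Fix one primary test whatever the cell counts.** A suitable sentence: 'VBAC success will be compared with a two-sided Barnard exact unconditional test (pooled score statistic) at 5%, whatever the cell counts; the risk difference will be reported with a 95% confidence interval from inversion of the same test.' The power to state is then about 56/72/89% at +20/+22.5/+25 with 30 per arm. The test must be named, because exact unconditional tests differ: Boschloo's gives 50/67/85% in the same setting.
3. **If the present rule is kept,** state observed or expected counts, continuity correction and sidedness, and restate its power (two-sided at 30:30, uncorrected: 42/57/75% or 49/61/75%).

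The cost is two or three sentences and no extra patients; the test is in standard software. Barnard's downsides are that clinical readers know it less well, it gains only 0-2 points over the observed-count rule at 29/31, and it falls below the expected-count rule (by up to 2.5 points) in about 12% of allocations at +20. It also leaves 80% unmet until a CSE rate of about 97.7% at 30:30.

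### The adjusted analysis of VBAC success names logistic regression with no sparse-data method, although only about 8 to 11 failures are expected under the plan's own rates

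*Combined protocol and SAP*

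**What the plan says.** All of this is in the combined protocol and SAP.

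- **Data Analysis Plan, Primary Outcome.** VBAC success is compared between arms by chi-square, or by "Fisher Exact test, in case of cell sizes <5". The next sentence adds the adjusted model: "Logistic regression analysis will be used to adjust for potential confounders and other factors associated with success or failure of VBAC". It names no estimator, no covariates, no limit on their number, and no method for few failures.
- **Secondary Outcomes.** The chi-square/Fisher pair is named again for the categorical secondary outcomes. Those are also unadjusted comparisons.
- **Power Analysis.** "The success rate of VBAC is around 74"%, and "we expect the success rate with CSE to increase by 20-25"%; then "given our sample size of 60, we will have 80% power to detect a difference between the two groups". It does not say whether the increase is absolute or relative, and gives no alpha or sidedness.
- **Summary of Project.** The design is described as "randomizing 60 eligible women into either an epidural group or CSE group", with no allocation ratio.
- **Background.** "Predictors for success of VBAC include previous spontaneous vaginal birth, singleton pregnancy, and previous low transverse scar". Previous spontaneous vaginal delivery (SVD) is also in the list of data to be collected.

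**The concern.** The authors foresaw small cells and provided for them in the unadjusted tests, but not in the adjusted model, where small cells do more damage. With very few failures, ordinary logistic regression has two weaknesses. If one arm has no failures, the fitted treatment log odds ratio runs off to infinity. If the fit is finite but several covariates are included, the estimate tends to be too far from the null.

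At stake are the adjusted odds ratio and its interval, which a pilot would be expected to pass on to a later trial. Without a named method, a remedy (penalisation, exact methods, dropping covariates) would have to be chosen after the data are seen.

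**Working it through.** **Inputs.** From Power Analysis: 60 women, 74% success with epidural, and a 20-25% increase with CSE. Assumed because not stated: 30 per arm, two-sided 5%, no dropout.

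**The plan's own figure.** The pooled normal-approximation sample size per arm is [1.96·√(2·p̄·q̄) + 0.842·√(p₁q₁ + p₂q₂)]² / (p₂ − p₁)². For 74% versus 99%, p̄ = 0.865, which gives (0.947 + 0.379)² / 0.0625 ≈ 28.1. That is 29 per arm, 58 in total, and power at 60 is 82.6%. The stated 80% is therefore reproduced, but only at the top of the range. Power is 56% at 94%, and 31% to 48% if the increase is relative (88.8% to 92.5%).

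**Expected failures and the chance of an empty CSE failure cell.** Expected failures = 30 × 0.26 + 30 × (1 − p), where p is the CSE success rate. The chance of no CSE failures is p³⁰.

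| Reading of the increase | CSE success | Expected failures | Chance of no CSE failures |
|---|---|---|---|
| Relative, 20% | 88.8% | 7.8 + 3.36 = 11.2 | 2.8% |
| Relative, 25% | 92.5% | 7.8 + 2.25 = 10.1 | 9.6% |
| Absolute, 20 points | 94% | 7.8 + 1.8 = 9.6 | 15.6% |
| Absolute, 25 points | 99% | 7.8 + 0.3 = 8.1 | 74.0% |
| No effect | 74% | 7.8 + 7.8 = 15.6 | 0.01% |

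A 27/33 split moves the 15.6% to 13-19% and the 74% to 72-76%.

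**How often the plan's own small-cell trigger is met.** The chance of a cell below 5 is 78%, 94%, 97% and over 99% for the first four rows. Fisher's test would usually be invoked, while the adjusted model has no counterpart.

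**Failures per parameter.** Treatment plus one covariate leaves 8.1/2 to 11.2/2, about 4.0 to 5.6. Treatment plus five covariates leaves 8.1/6 to 11.2/6, which is below 2.

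**Example: failures 8/30 (epidural) versus 0/30 (CSE), unadjusted.**

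- Fisher: p = 0.0046.
- Ordinary likelihood-ratio test: chi-square 12.33, p = 0.0004. The profile upper limit for the odds ratio of failure is 0.21. There is no finite estimate and no lower limit.
- Firth: odds ratio 0.043 (95% CI 0.0003-0.38), p = 0.0017.

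**Bias when the fit is finite.** In simulation with five covariates (their properties are assumptions, not document figures), the median ordinary log odds ratio of failure was −1.25 against a true −1.02 at CSE 88.8%, and −2.04 against −1.71 at 94%. As odds ratios (exponentials) these are about 0.29 against 0.36, and 0.13 against 0.18. Firth estimates stayed finite and close to the truth.

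**Effect of one covariate.** Adding previous SVD (assumed prevalence 30%, odds ratio of failure 0.25 or 0.5) at CSE 94% left the treatment odds ratio non-finite in 15-16% of ordinary fits, about the same as with no covariate. Some coefficient was non-finite in 27-40%. With no effect, rejection rates were 5.2-5.4% for Firth and 5.8-6.5% for the ordinary likelihood-ratio test.

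**The case against.** **Little is lost.** The test named for deciding significance is chi-square or Fisher, and it is untouched. Even with no CSE failures, the table, Fisher p-value, likelihood-ratio p-value and upper limit can be reported. This stands, and it is why the point is minor. A reader might infer that the primary analysis is compromised; it is not.

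**Logistic regression does not exclude Firth.** This is correct, as ordinary maximum likelihood is an assumption here. The gap is one of specification rather than a wrong method stated. It still leaves the choice until after the data are seen, and the example shows that the choice changes what is reported.

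**Firth adds little precision.** Its interval in the example is very wide, and its upper limit (0.38) is less tight than the ordinary 0.21. The test-size gain is modest. All of this stands. The gain is a finite, less biased estimate and a rule fixed in advance.

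**A larger figure is tempting.** A reader might assume that the 80% power claim is true, solve for the CSE rate that makes it so, and conclude that the adjusted estimate would be lost in a third to three fifths of trials. The documents do not support that. The answer depends on the test used for the back-calculation: 33% (CSE 96.4%, one-sided), 40% (97.0%, uncorrected chi-square) or 62% (98.4%, two-sided normal approximation). None of these is the planned rule. Switching to Fisher when a cell is below 5 reaches 80% only at about 99.65%, outside the planned range, where the chance of no CSE failures is 0.9965³⁰ ≈ 90%. The rates that the plan states are the sound basis.

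**Post-randomisation covariates.** The covariate wording is open enough that a reader might infer that adjustment for events after the block is planned. No section commits to that, so the restriction in the fix is a precaution.

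**Conclusion.** The point holds as a minor, cheap improvement. The plan commits to an adjusted logistic model without a sparse-data method, while its own rates imply about 8 to 11 failures. The chance that the ordinary treatment odds ratio and its lower limit do not exist is 3-10% on the relative reading, 16% to 74% on the absolute reading, and negligible with no effect. The 74% requires CSE success to be almost complete. With several covariates, the ordinary estimate also overstates the effect.

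This rests on equal allocation, full enrolment of 60, ordinary maximum likelihood, and the planned rates being near the truth. Calling the model supporting is a fair reading, not the plan's own label. The documents do not support a rule of exactly one covariate: how many and which to use is a trade-off for the investigators, and a separate matter from the missing method.

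**What to change.** Replace the logistic regression sentence under Primary Outcome with:

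> A supporting adjusted analysis of VBAC success will use Firth penalised logistic regression with penalised profile-likelihood confidence intervals and p-value, adjusting for a small number of pre-named variables fixed before randomisation (for example previous SVD).

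Previous SVD is offered as an example because it is already collected, is fixed before randomisation, and is listed in Background as a predictor of success. The investigators should choose the variables and name them in advance.

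The cost is SAP wording only: no new data field, no change to the primary test or sample size, and Firth regression is in standard software. The downside is that fewer covariates can be examined than the open wording allows, and the adjusted estimate will remain imprecise.

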Inclusion criteria: (all patients meeting ACOG guidelines for TOLAC) ASA II Patients 18 years of age or more with at least one previous elective cesarean delivery, <40 weeks gestational age (GA), vertex singleton pregnancy with use of continuous fetal monitoring.

Exclusion criteria: Patients undergoing TOLAC but refusing regional anesthetic or with contraindication for regional anesthesia, less than 18 years of age, BMI >40 or with associated comorbidities such as gestational diabetes, preeclampsia, abnormal placenta, etc.

Specific outcomes to be looked at include:

Primary outcome:

- Success of vaginal birth after cesarean (VBAC)

Secondary outcomes:

- Success of analgesia/ maternal satisfaction (self- rated pain score of 1-10 prior to, 30 minutes after the regional anesthetic is performed and 24 hrs post-delivery)
- If requiring a repeat C-section or instrumental delivery the success of regional anesthesia for the procedure. (self- rated pain score of 1-10 and necessity to use additional IV pain medication or conversion to general/ spinal anesthesia)
- Immediate side effects: fetal bradycardia, nausea, vomiting, pruritus, hypotension requiring vasopressors
- Late side effects i.e. post dural puncture headache

Methods:

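### The pain-score ANOVA leaves out the planned pre-block score: the test is valid for one score per woman but gives up precision that would cost almost nothing to recover

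*Combined protocol and SAP*

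**What the plan says.** Under Data Analysis Plan, Secondary Outcomes, the method for pain is: "The secondary outcome, success of analgesia, as measured by pain score on a scale of 1 to 10, will be assessed using ANOVA". The model is then spelled out, with "pain score as the dependent variable and analgesia group as the independent variable". Group is its only term.

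A score before the block is planned in three places:
- The list of secondary outcomes has a "self- rated pain score of 1-10 prior to, 30 minutes after the regional anesthetic is performed and 24 hrs post-delivery".
- Methods states: "Self-determined numeric pain scores will be obtained prior to and after placement of the regional anesthetic and after delivery by nursing staff".
- The data-collection section refers to "pain scores obtained prior to and following placement of the regional anesthetic". Its itemised list has a score before the block, then "15 minutes, 30 minutes, and 60 minutes after RA", then one 24 hours after delivery.

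Covariate adjustment is planned for another endpoint. For VBAC, under Primary Outcome, "Logistic regression analysis will be used to adjust for potential confounders" and other prognostic factors. No such provision is made for pain.

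**The concern.** A woman's pain before the block may predict her pain afterwards. If it does, leaving it out keeps explainable variation in the error term, and the comparison is less precise than the planned data allow. That matters more in a trial limited to 60 women.

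There is a second effect. If the arms happen to differ in starting pain, about r times that difference stays in the unadjusted estimate (taking equal SDs before and after). The standard error already allows for this, so it is not bias, but naming the covariate in advance would remove it. Adding the covariate only after the data are seen would leave a choice between two results.

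Only the pain comparison is at stake.

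**Working it through.** **Inputs.** The total of 60 women comes from the project summary. The allocation ratio is not stated, so 30 per arm is assumed. Two-sided alpha of 0.05 is also assumed. The protocol gives no SD, target difference, power or pre/post correlation for pain, so there is no stated figure to reproduce and r is varied. The only power statement concerns VBAC.

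**Variance ratio.** Adjusting for a baseline score with correlation r removes a share r² of the variance. Estimating the slope adds a factor 1 + 1/(N − 4). With N = 60 this is 1 + 1/56 = 1.0179, so

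ratio (ANCOVA/ANOVA) = (1 − r²) × 1.0179.

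For example, at r = 0.3 it is 0.91 × 1.0179 = 0.926, and at r = 0.5 it is 0.75 × 1.0179 = 0.763. The number of unadjusted women giving equal precision is 60/ratio.

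**Power.** The unadjusted test (58 error df) has 80% power at a difference of about 0.74 SD. Power of the adjusted test at that same difference comes from the noncentral t with 57 df.

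| r | Variance ratio | Equivalent unadjusted N | CI width ratio | Adjusted power |
|---|---|---|---|---|
| 0 | 1.018 | 58.9 | 1.009 | 79% |
| 0.1 | 1.008 | 59.5 | 1.004 | 80% |
| 0.2 | 0.977 | 61.4 | 0.989 | 81% |
| 0.3 | 0.926 | 64.8 | 0.963 | 83% |
| 0.4 | 0.855 | 70.2 | 0.925 | 86% |
| 0.5 | 0.763 | 78.6 | 0.874 | 89% |

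Break-even is where (1 − r²) × 1.0179 = 1, that is r = √(1 − 1/1.0179) = 0.13.

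**Validity.** Null trials were simulated with scores rounded and cut to 1–10 (20,000 per setting, r from 0 to 0.7). The group-only test of one score per woman rejected in 4.7% to 5.2% of trials and the adjusted test in 4.7% to 5.3%. Both hold the nominal 5%.

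**Floor effects.** An effective block pushes many post-block scores to the bottom of the scale, which weakens the correlation. A second simulation (10,000 trials per setting) assumed a pre-block mean of 7 and SD of 2, and an underlying post-block mean of 1 and SD of 2, which puts about 60% of post-block scores at the floor. An underlying r of 0.3 became an observed 0.24 (ratio 0.95), and 0.5 became 0.40 (ratio 0.86). At r = 0 the ratio was 1.02. Type I error was 4.8% to 5.3% for both methods.

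**Chance imbalance in starting pain.** The standard error of the baseline difference is SD × √(2/30). The SDs are assumed.

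| SD | Standard error | Chance of a difference of 1 point or more |
|---|---|---|
| 1.5 | 0.39 | 1% |
| 2 | 0.52 | 5% |
| 2.5 | 0.65 | 12% |

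Of a 1-point imbalance, r × 1 point reaches the unadjusted estimate: 0 to 0.5 point for r from 0 to 0.5.

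**The case against.** The strongest reply is that nothing here is an error. The planned test is valid, pain is a secondary outcome in a self-described pilot, and no stated power figure for pain fails. All of that stands, and it limits the point to a modest improvement.

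Next, the gain rests on an r that the protocol does not give. Below 0.13 adjustment loses slightly, and at 0.2 it gains only about 2% of variance. The floor share is also assumed: with 80% of scores at the floor, an underlying r of 0.3 would fall to about 0.20 and the ratio would be about 0.98. Women are screened when they ask for neuraxial analgesia, which may narrow the range of starting pain and lower r further. This is fair, and no particular gain can be promised. But the downside is capped at an interval about 1% wider, and the upside is not similarly capped.

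The correlation with pain 24 hours after delivery may be weaker still. That also stands, and the same 1% cap applies.

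Finally, validity is shown only for one score per woman, and the plan does not say which of the post-block scores is the dependent variable. Stacking several in a group-only model with no within-woman term would inflate type I error. In simulation it reached 7% to 11% with two scores and 12% to 21% with four, at within-woman correlations of 0.2 to 0.5. That is a separate and potentially larger gap. It does not weaken the case for the covariate, and the fix below closes it. Methods also sets a cut-off score for successful analgesia while the analysis compares means; the covariate does not resolve that.

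**Conclusion.** The point holds. The stated pain model omits a baseline score that the trial already plans to collect. With one post-block score per woman the test is valid, and the omission may cost precision. Assuming 30 per arm, including the score would be worth about 5 extra women at r = 0.3 and 19 at r = 0.5, and less if many scores sit at the floor. If r is below about 0.13 there is nothing to gain, and the most that can be lost is about 1% of interval width. The change is worth making because the cost is small and bounded, not because a large gain is assured. The VBAC analysis and its conclusions do not depend on it.

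**What to change.** In Data Analysis Plan, Secondary Outcomes, replace the group-only ANOVA with an ANCOVA of the 30-minute score on analgesia group, with the pre-block score as covariate. Thirty minutes is a time the protocol's own outcome list already names. Analyse the 24-hour post-delivery score in a separate model of the same form, and state which of the two is the main pain comparison.

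If several post-block times are to be analysed together, use a mixed model with group, time, group-by-time, the pre-block score and a random effect for woman. A pre-block-by-time term can be added if the baseline relation is expected to weaken over time.

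The cost is about one line of SAP wording and one of 58 error degrees of freedom per single-time model. No new data are needed, and the change should be fixed before outcomes are examined.
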